#### 9.7.2.5 Sensitivity Analysis

None planned

9.7.2.6 Subgroup Analysis

None planned

#### 9.7.2.7 Stratified Analysis

For the secondary objective of describing health and developmental outcomes in infants up to 12 months of age, analyses will be stratified according to whether the infant was exposed to Repatha® (in the 15 weeks prior to conception or in the first trimester of pregnancy, in the second or third trimester of pregnancy, and/or whilst breast-feeding). In addition, a stratified analysis will be conducted by exposure to other lipid modifying therapies (including statins, PCSK9 inhibitors, CETP inhibitors, and others).

In addition, data obtained from retrospective and prospective subject identification will be reported separately (to account for the possibility that subjects enrolled retrospectively may differ from those enrolled prospectively).

Results from mothers are to be presented using the following columns: (i) 'unexposed', (ii) 'exposed but stopped prior to conception', (iii) 'exposure in 1st trimester (up to 15 weeks)', (iv) 'exposure in 2nd/3rd trimesters', (v) 'exposed at conception and during 1st trimester but stopped during 2nd/3rd trimesters, (vi) 'exposed throughout pregnancy', (vii) 'exposure during breastfeeding only', and (viii) 'exposure anytime during pregnancy and up to 15 weeks, and breastfeeding'. Columns will not be mutually exclusive.

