Moreover, nonclinical studies have shown that administration of Repatha® to pregnant cynomolgus monkeys throughout gestation (at exposure levels12-times higher than patients receiving Repatha® at 420 mg QM) resulted in no effects on embryo-fetal/neonatal growth and development through to 6 months postpartum (Evolocumab Investigator's Brochure 2015). However, clinical data of Repatha® use in pregnancy is limited, therefore safety of Repatha® in pregnancy is considered to be missing information and this is reflected in the SmPC.

The SmPC states the following on use of Repatha® in association with pregnancy:

- There are no or limited amount of data from the use of Repatha® in pregnant women. Animal studies do not indicate direct or indirect effects with respect to reproductive toxicity.
- Repatha® should not be used during pregnancy unless the clinical condition of the woman requires treatment with evolocumab.

**Similarly, s**afety of Repatha® whilst breast-feeding is considered to be missing information. Published literature **indicates** that **in general**, there is a low risk of maternally-administered monoclonal antibodies resulting in pharmacologically relevant systemic exposures in breastfed infants, the milk-to-serum concentration ratio of IgGs being low (Kim et al, 1992; Telemo et al., 1996; Ostensen and Eigenmann, 2004; Mahadevan et al, 2005; Vasiliauskas et al, 2006). In studies of breast-feeding women treated with other therapeutic monoclonal antibodies, these antibodies were not present in breast milk at detectable concentrations (Vasiliauskas et al, 2006, Kane and Acquah, 2009). In addition, large molecules are known to have low oral bioavailability in the infant gastrointestinal tract (Van de Perre, 2003; Lobo et al, 2004; Hurley and Theil, 2011).

The SmPC states the following on use of Repatha® whilst breast-feeding:

- It is unknown whether evolocumab is excreted in human milk.
- A risk to breastfed newborns/infants cannot be excluded.

A decision must be made whether to discontinue breast-feeding or discontinue/abstain from Repatha® therapy taking into account the benefit of breast-feeding for the child and the benefit of therapy for the woman.

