#### 7.2 Rationale

In light of the limited data available on use of Repatha® in association with pregnancy and/or lactation, this study is being conducted in response to a request by the EMA to

provide data on outcomes of pregnancy in women (and their infants to the age of 12 months) exposed to Repatha® prior to or during pregnancy and/or breast-feeding.

In women of child-bearing age in Europe, South Africa and Australia those most likely to have been identified as requiring Repatha® for control of hypercholesterolaemia are those diagnosed with FH. Introduction of this particular pharmacological intervention in the majority of non-FH women is anticipated to occur beyond reproductive age.

Considering the low rate of FH diagnosis and the small number of Repatha®-exposed pregnancies anticipated to occur, routine pharmacovigilance surveillance based solely on spontaneous reporting is unlikely to provide the information required by the EMA, in the post-launch period. To address this, a separate study is required, with a targeted, proactive approach to identify cases and seek appropriate follow-up of outcomes of pregnancy in women with FH who have received Repatha® during pregnancy and/or breast-feeding.

This multinational observational study is expected to enrol female FH patients, identified in collaboration with specialist physicians and patient groups:

- Females with FH exposed to Repatha® during pregnancy and/or breast-feeding will form the exposed cohort, and
- Females with FH unexposed to Repatha® during pregnancy and breast-feeding will form the internal comparator group. Although no formal comparison of exposed/unexposed subjects is planned, capturing outcomes of pregnancy in a rare population unexposed to Repatha® will provide contemporary reference **data** against which to consider outcomes in exposed pregnancies.

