#### 8.2 Secondary Objectives

- To describe outcomes of pregnancy (other than congenital anomalies) in females with FH exposed to Repatha® within 15 weeks prior to or during pregnancy
- To describe outcomes of pregnancy in females with FH not exposed to Repatha® within 15 weeks prior to or during pregnancy
- To describe **health and developmental** outcomes in infants up to the age of 12 months, born to females diagnosed with FH and **unexposed or** exposed to Repatha® **during pregnancy and/or breastfeeding.**

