    - Infant(s) sex
    - Gestational age
    - Birth weight
    - Apgar score
  - Infant outcomes until 12 months of age:
    - Weight growth
    - Developmental delay (not meeting the usual developmental milestones during the first 12 months of age)
    - Hospitalisations (total number of days hospitalised; number of hospitalisation episodes during the first 12 months)
    - Chronic medication (defined as medication prescribed for a period of 4 weeks or more)
    - Breastfeeding (date of start/stop, exclusive breastfeeding [Yes/No])
- Exposure Variables:
  - Exposure to Repatha® (duration of exposure, doses, dose dates) within 15 weeks prior to conception and/or during pregnancy and/or whilst breast-feeding. In adult subjects a single dose of Repatha® constitutes exposure. In infants, exposure may occur in utero and/or via breast milk, within 15 weeks following the date of Repatha® dosing in the mother.

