## 9.7.2.3.2 Description of Subject Characteristics

Subjects are women diagnosed with FH, treated at centres in Europe, South Africa and Australia, with pregnancy confirmed during the study observation period and who provide informed consent to participate in the study.

Exposed subjects are women who received Repatha® during pregnancy and/or breast-feeding; unexposed subjects are women who have not received Repatha® during pregnancy and/or breast-feeding. In infants, exposure may occur in utero and/or via breast milk, within 15 weeks following the date of Repatha® dosing in the mother.

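### Infant outcomes are not split by feeding mode, so milk exposure to Repatha cannot be told apart from breast-feeding itself when milk-exposed infants are read beside unexposed infants

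*Supplement*

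**What the plan says.** The third secondary objective (Section 8.2) is to describe health and developmental "outcomes in infants up to the age of 12 months, born to females diagnosed with FH", whether exposed to Repatha or not in pregnancy or breast-feeding.

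For this objective, Section 9.7.2.7 states that "analyses will be stratified according to whether the infant was exposed to Repatha". The windows are before conception or first trimester, second or third trimester, and breast-feeding, and they may overlap. The same section adds that "a stratified analysis will be conducted by exposure to other lipid modifying therapies" and that "data obtained from retrospective and prospective subject identification will be reported separately".

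Section 9.7.2.3.2 gives the routes of infant exposure: "In infants, exposure may occur in utero and/or via breast milk, within 15 weeks following the date of Repatha" dosing in the mother. Section 7.2 defines the comparator by absence of the drug: women with FH not exposed to Repatha "during pregnancy and breast-feeding will form the internal comparator group". Section 9.2.3 makes pregnancy, not feeding, the basis of eligibility and lists no exclusions.

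Feeding is recorded. Section 9.3 lists, among infant outcomes to 12 months, "Breastfeeding (date of start/stop, exclusive breastfeeding [Yes/No"]). No stratum, column or subgroup uses it to form a reference. Sections 9.7.2.5 and 9.7.2.6 plan no sensitivity or subgroup analyses, and the checklist in Appendix B treats confounding as not applicable because the study is descriptive.

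**The concern.** An infant can enter the milk stratum only by being breast-fed. An infant enters the unexposed group because the mother took no Repatha, whatever the feeding. The two groups therefore differ in drug exposure and in feeding mode together, and this is built into the definitions rather than being a chance imbalance.

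Weight growth, hospitalisation and chronic medication may differ by feeding mode, or by whether an infant was well enough to be breast-fed, without any drug effect. The protocol gives missing information on safety during breast-feeding as one reason for the study (Sections 7.1 and 7.2). The milk stratum is where that question is addressed, and as planned it has no like-for-like reference. The risk is a table that wrongly reassures or wrongly alarms.

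**Working it through.** **No figure to reproduce.** The documents state no event rate, sample size or precision for infant outcomes, so the check is of the definitions, followed by an illustration.

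**Definitions side by side**

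| Group | How an infant enters | Feeding mode |
|---|---|---|
| Milk stratum (9.7.2.7, 9.7.2.3.2) | Receives breast milk within the exposure window after a maternal dose | All breast-fed |
| Unexposed (7.2, 9.2.3) | Mother with FH had no Repatha in pregnancy or breast-feeding | Unrestricted |

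The two further breakdowns in Section 9.7.2.7, by other lipid-modifying therapy and by identification mode, leave this contrast unchanged within each of their levels.

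**Illustration.** Let

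- p = share of unexposed infants who are breast-fed (assumed; not in the documents);
- r = outcome risk in infants not breast-fed divided by that in breast-fed infants (assumed; not in the documents).

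With no drug effect, and risk in breast-fed infants set to 1, the milk stratum has risk 1 and the pooled unexposed group has risk p + (1 − p)·r. The apparent ratio is

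1 / [p + (1 − p)·r].

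For r = 1.5:

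- p = 0.5: 1 / (0.5 + 0.5 × 1.5) = 1 / 1.25 = 0.80
- p = 0.8: 1 / (0.8 + 0.2 × 1.5) = 1 / 1.10 = 0.91

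Over a range of r:

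| r | p = 0.5 | p = 0.8 |
|---|---|---|
| 0.8 | 1.11 | 1.04 |
| 1.0 | 1.00 | 1.00 |
| 1.25 | 0.89 | 0.95 |
| 1.5 | 0.80 | 0.91 |
| 2.0 | 0.67 | 0.83 |

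The distortion changes sign at r = 1 and also vanishes if p = 1.

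**Masking.** A true drug ratio of 1.3 with r = 1.5 would appear as 1.3 / 1.25 = 1.04 at p = 0.5 and 1.3 / 1.10 = 1.18 at p = 0.8.

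**After the fix.** Against breast-fed unexposed infants only, both groups have risk 1 when the drug has no effect, so the ratio is 1.00 for every p and r in this simple model.

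**Size of the new reference.** Section 9.5 caps unexposed pregnancies at 600. If each gave one followed infant (an upper bound, apart from multiple births), the breast-fed reference would number 600 × 0.5 = 300 to 600 × 0.8 = 480.

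**The case against.** **The study only describes.** Sections 7.3 and 9.7.2.4 rule out inference and any formal comparison of exposed with unexposed, so the plan will produce no ratio. The infant sentence in 9.7.2.7 names no reference column. This stands, and it limits the point to how tables are read. It does not remove it: Section 7.2 calls the unexposed group the internal comparator and reference data, and the third secondary objective describes exposed and unexposed infants together.

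**Small numbers would hide the effect.** Suppose 30 to 50 milk-exposed infants, with hospitalisation of 10% if breast-fed and 15% if not (all assumed). The pooled reference is then 11.0–12.5%, a gap of 1 to 2.5 points, or 30 × 0.01 = 0.3 to 50 × 0.025 = 1.25 infants. This is fair as to practical weight, but a small stratum is no reason to give it a mismatched reference.

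**Feeding may be reported anyway.** Because breast-feeding is listed among the infant outcomes, its frequency may appear in each stratum. That would reveal an imbalance but would not give the outcomes of breast-fed unexposed infants.

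**The in-utero strata.** A reader might infer that infants exposed only in utero are breast-fed less often than unexposed infants, and so look worse, because of the label text in Section 7.1: "A decision must be made whether to discontinue breast-feeding or discontinue/abstain from Repatha". The text offers two options. A woman treated in pregnancy who then abstains and breast-feeds leaves a breast-fed infant in the in-utero stratum. The documents do not support a lower breast-feeding rate there. Splitting those infants by feeding would also condition on something that happens after the exposure and may depend on it, which can itself introduce selection bias. The milk stratum is different: its definition already restricts to breast-fed infants, and the reference merely needs to match.

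**Conclusion.** The point holds for the milk stratum. As planned, a side-by-side reading of milk-exposed and unexposed infants cannot separate Repatha in milk from breast-feeding. The further breakdowns in Section 9.7.2.7 do not touch feeding mode, so it would be wrong to say that infants are stratified by Repatha alone, but the gap remains.

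Direction and size are unknown. The 0.80–0.91 range rests wholly on the assumed r = 1.5 and p = 0.5–0.8. A reader might infer that the milk stratum will look too favourable; the documents give no rates by feeding mode, and if r is below 1 the distortion runs the other way.

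Nor is this a biased test or a threat to the primary objective on congenital anomalies. It is a cheaply mended weakness in the display for one descriptive secondary objective.

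**What to change.** In Section 9.7.2.7:

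- Use the breast-feeding start and stop data from Section 9.3 to split unexposed infants into ever and never breast-fed, and show the ever breast-fed as the reference column beside the milk stratum.
- Keep the all-unexposed column for the in-utero strata.
- Report the share breast-fed in every stratum. Duration and exclusivity, also collected, could be added, because ever/never does not capture them.

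No new data, visits or enrolment are needed. The cost is one more split of the infant tables and smaller cells in the unexposed reference. The split handles feeding mode only; other differences between milk-exposed and unexposed infants remain.

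### For infants whose mother first doses some time into breast-feeding, admissions and chronic medication that began before that dose are counted in the breast-feeding stratum

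*Supplement*

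**What the plan says.** **Stratum (9.7.2.7).** Infant health and developmental outcomes are stratified by whether the infant was exposed, with windows around conception and the first trimester, then "in the second or third trimester of pregnancy, and/or whilst breast-feeding". Mothers are tabulated separately, and maternal column (vii) is "exposure during breastfeeding only".

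**Exposure (9.3).** "In adult subjects a single dose of Repatha" is enough to count as exposure. For the child, "In infants, exposure may occur in utero and/or via breast milk, within 15 weeks following the date of Repatha" dosing in the mother.

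**Outcome window (9.3).** The list is headed "Infant outcomes until 12 months of age". Hospitalisation is recorded as "total number of days hospitalised; number of hospitalisation episodes during the first 12 months". Chronic medication is "defined as medication prescribed for a period of 4 weeks or more" and takes its window from the list heading. Section 9.3.2 adds assessments at 6 and 12 months, counted from delivery.

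**Dates.** Maternal dose dates are collected, as are feeding dates ("date of start/stop, exclusive breastfeeding"). Section 9.3 names no admission date or medication start date for the infant. The eCRF is not shown and may hold them.

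**Other analyses.** Sections 9.7.2.5 and 9.7.2.7.2 plan no sensitivity analysis, 9.7.2.7.1 calls one for bias not applicable, and 9.7.3 plans no further safety analysis.

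**The concern.** The stratum label is set by whether milk exposure happened, but the outcome is counted from birth. Where milk exposure starts some time after birth, the stratum takes in events that came first. A neonatal admission is the plainest example: it precedes any dose given after delivery.

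The protocol calls safety during breast-feeding missing information, and infant outcomes by breast-feeding exposure are a secondary objective. With no model behind them, the tabulated counts are the result. If the stratum is small, one or two misplaced admissions could change how it reads.

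**Working it through.** The plan states no figure on this point, so the check sets the definitions against each other.

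**Step 1. Date the exposure.** Let b be the infant's age when feeding starts. Let d be the age at the first maternal dose whose 15-week window overlaps feeding (negative if the dose came before birth). First milk exposure is at s = max(b, d). Milk could have contributed only to an event that begins at age t ≥ s. The 12-month total counts every t from 0 to 12 months.

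**Step 2. Apply this to the possible histories.**

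- *Dose within 15 weeks before feeding, feeding from birth:* s = 0. No event is misplaced. This includes mothers who dosed late in pregnancy.
- *No dose in the 15 weeks before feeding, first later dose at month 4 while feeding:* s = 4 months. An admission in week 1 is counted in the milk stratum.
- *Column (vii) mothers:* with no pregnancy exposure, the first relevant dose follows delivery, so s > 0. The gap may be days or months; the documents do not say.
- *Early exposure, stopped, then restarted while feeding:* the same timing problem arises for the milk stratum. Because the windows are joined by and/or, the infant may also appear in an in-utero stratum, where the early events do follow exposure.

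**Step 3. Look for a rule that removes the early events.** None appears in 9.3, 9.3.2, 9.7.2.5 or 9.7.2.7 to 9.7.3. The 6-month assessment gives a split by age, not by exposure.

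**Step 4. Illustrate the size. Every input here is assumed.** Let f be the fraction of the stratum's infants who start late, and g the share of a late starter's 12-month events that fall before s. Assume equal expected events per infant and no exposure effect. The misplaced share of the stratum's events is then f × g.

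- Flat event rate: g = s/12, so s = 1, 3, 6 months gives 0.083, 0.25, 0.50.
- Half of events in months 0–3: g = 0.5 × s/3 for s ≤ 3, then 0.5 + 0.5 × (s − 3)/9. This gives 0.167, 0.50, 0.667.

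| f | Flat: s = 1, 3, 6 | Early-weighted: s = 1, 3, 6 |
|---|---|---|
| 0% | 0%, 0%, 0% | 0%, 0%, 0% |
| 10% | 0.8%, 2.5%, 5.0% | 1.7%, 5.0%, 6.7% |
| 25% | 2.1%, 6.3%, 12.5% | 4.2%, 12.5%, 16.7% |
| 50% | 4.2%, 12.5%, 25.0% | 8.3%, 25.0%, 33.3% |

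The spread reflects the assumptions. It does not estimate what this study will see.

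**The case against.** **Counting rules belong in an SAP, and none is shown.** Appendix G is only an example template and covers pregnancy outcomes, so no infant table can be inspected. A timing rule could exist elsewhere. This stands in part. The protocol itself fixes both the grouping and the 12-month window, so such a rule would have to add to what 9.3 and 9.7.2.7 say.

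**A reader might infer that the protocol declares an ever-exposed classification.** It does not use that term. The single-dose sentence concerns adults, and infants have their own 15-week definition. The classification is inferred from grouping by whether exposure occurred. The 15-week rule could be used to date exposure, but nothing applies it to the timing of outcomes.

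**The affected group may be empty.** The label, quoted in the Abstract and 7.1, asks women to choose between feeding and treatment, and few exposed pregnancies are expected. Column (vii) shows that the protocol provides for mothers first exposed after delivery. It does not show that they will be many, or that they will start late. This stands and limits the size of the point.

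**Safety reports may already date the events.** Section 11.1.1 calls for all adverse events in exposed subjects, hospitalisation is a serious criterion in 11.1.2, and the Appendix C form carries event start dates. With few infants, timing could be checked case by case. That helps interpretation but leaves the planned stratified counts as they are, because 9.7.3 adds no analysis of those reports.

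**No inference is at risk.** Section 9.7.2.4 plans no formal comparison. This stands.

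**Conclusion.** The point holds in a narrow form. Under 9.3 and 9.7.2.7 as written, admissions and chronic medications that began before first milk exposure are counted in the breast-feeding stratum. The infants concerned are those whose mother had no dose in the 15 weeks before feeding began and first dosed later while feeding, chiefly the infants of column (vii) mothers. This rests on reading the stratum as a yes/no label and on no timing rule existing in a document not shown.

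The number affected is unknown and may be zero. A reader might take the larger illustrative percentages as the expected distortion, or conclude that an exposed/unexposed comparison is biased. The documents support neither: they give no frequency or timing of late starts, and no formal comparison is planned. The consequence is limited to how descriptive counts are read. A change is still worth making because it is cheap and bears on a stated information gap.

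**What to change.** In 9.7.2.7, for the breast-feeding stratum, report hospitalisations and chronic medications that began on or after first milk exposure separately from those that began earlier. Define first milk exposure as the later of feeding start and the first maternal dose whose 15-week window overlaps feeding. Keep the 12-month total as a companion row. If the stratum holds only a few infants, a listing of each event's start date against first milk exposure does the same job.

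Confirm that the eCRF records admission dates and medication start dates for all infants. Infant-months for each period and an age-matched unexposed row are optional; the point does not depend on them.

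The cost is at most two date fields from notes already being abstracted, one extra split or listing, and a slightly smaller milk-exposed event count.

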		Exposed but stopped prior			Exposed at conception and during 1 st trimester	Exposed	Exposure during breastfeeding	
	Unexposed (N = x)	to conception (N = x)	trimester (N = x)	trimesters (N = x)	trimesters (N = x)	pregnancy (N = x)	only (N = x)	breastfeeding (N = x)
	(N – X) n (%)	(N – X) n (%)	(N – X) n (%)	(N – X) n (%)	(N – X) n (%)	(N – X) n (%)	(N – X) n (%)	(N – X) n (%)
Pregnancies enrolled pre-partum								
All outcomes	x (x.x)	x (x.x)	x (x.x)	x (x.x)	x (x.x)	x (x.x)	x (x.x)	x (x.x)
Live birth without congenital anomaly	x (x.x)	x (x.x)	x (x.x)	x (x.x)	x (x.x)	x (x.x)	x (x.x)	x (x.x)
Live birth with congenital anomaly	x (x.x)	x (x.x)	x (x.x)	x (x.x)	x (x.x)	x (x.x)	x (x.x)	x (x.x)
Neonatal death without congenital anomaly	x (x.x)	x (x.x)	x (x.x)	x (x.x)	x (x.x)	x (x.x)	x (x.x)	x (x.x)
Neonatal death with congenital anomaly	x (x.x)	x (x.x)	x (x.x)	x (x.x)	x (x.x)	x (x.x)	x (x.x)	x (x.x)
Stillbirth without congenital anomaly	x (x.x)	x (x.x)	x (x.x)	x (x.x)	x (x.x)	x (x.x)	x (x.x)	x (x.x)
Stillbirth with congenital anomaly	x (x.x)	x (x.x)	x (x.x)	x (x.x)	x (x.x)	x (x.x)	x (x.x)	x (x.x)
Miscarriage without congenital anomaly	x (x.x)	x (x.x)	x (x.x)	x (x.x)	x (x.x)	x (x.x)	x (x.x)	x (x.x)
Miscarriage with congenital anomaly	x (x.x)	x (x.x)	x (x.x)	x (x.x)	x (x.x)	x (x.x)	x (x.x)	x (x.x)
Termination of pregnancy without congenital anomaly	x (x.x)	x (x.x)	x (x.x)	x (x.x)	x (x.x)	x (x.x)	x (x.x)	x (x.x)
Termination of pregnancy with congenital anomaly	x (x.x)	x (x.x)	x (x.x)	x (x.x)	x (x.x)	x (x.x)	x (x.x)	x (x.x)
Ectopic pregnancy	x (x.x)	x (x.x)	x (x.x)	x (x.x)	x (x.x)	x (x.x)	x (x.x)	x (x.x)
Molar pregnancy	x (x.x)	x (x.x)	x (x.x)	x (x.x)	x (x.x)	x (x.x)	x (x.x)	x (x.x)
Pregnancy continuing at time of data cut-off	x (x.x)	x (x.x)	x (x.x)	x (x.x)	x (x.x)	x (x.x)	x (x.x)	x (x.x)
Pregnancies enrolled post-partum	x (x.x)	x (x.x)	x (x.x)	x (x.x)	x (x.x)	x (x.x)	x (x.x)	x (x.x)
All outcomes	x (x.x)	x (x.x)	x (x.x)	x (x.x)	x (x.x)	x (x.x)	x (x.x)	x (x.x)
Live birth without congenital anomaly	x (x.x)	x (x.x)	x (x.x)	x (x.x)	x (x.x)	x (x.x)	x (x.x)	x (x.x)
Live birth with congenital anomaly	x (x.x)	x (x.x)	x (x.x)	x (x.x)	x (x.x)	x (x.x)	x (x.x)	x (x.x)
Neonatal death without congenital anomaly	x (x.x)	x (x.x)	x (x.x)	x (x.x)	x (x.x)	x (x.x)	x (x.x)	x (x.x)
Neonatal death with congenital anomaly	x (x.x)	x (x.x)	x (x.x)	x (x.x)	x (x.x)	x (x.x)	x (x.x)	x (x.x)

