## Appendix G. Template Summary Table of Pregnancy Outcome

			1	liming of Re	oatha ® expos	ure		
	Unexposed (N = x)	Exposed but stopped prior to conception (N = x)	Exposure in 1st trimester (N = x)	n Exposure ir 2 nd /3rd trimesters (N = x)	Exposed at conception and during 1 st trimester but stopped in 2nd/3rd trimesters (N = x)	Exposed	Exposure during breastfeeding only (N = x)	Exposure during both pregnancy and breastfeeding (N = x)
	n (%)	n (%)	n (%)	n (%)	n (%)	n (%)	n (%)	n (%)
Stillbirth without congenital anomaly	x (x.x)	x (x.x)	x (x.x)	x (x.x)	x (x.x)	x (x.x)	x (x.x)	x (x.x)
Stillbirth with congenital anomaly	x (x.x)	x (x.x)	x (x.x)	x (x.x)	x (x.x)	x (x.x)	x (x.x)	x (x.x)
Miscarriage without congenital anomaly	x (x.x)	x (x.x)	x (x.x)	x (x.x)	x (x.x)	x (x.x)	x (x.x)	x (x.x)
Miscarriage with congenital anomaly	x (x.x)	x (x.x)	x (x.x)	x (x.x)	x (x.x)	x (x.x)	x (x.x)	x (x.x)
Termination of pregnancy without congenital anomaly	x (x.x)	x (x.x)	x (x.x)	x (x.x)	x (x.x)	x (x.x)	x (x.x)	x (x.x)
Termination of pregnancy with congenital anomaly	x (x.x)	x (x.x)	x (x.x)	x (x.x)	x (x.x)	x (x.x)	x (x.x)	x (x.x)
Ectopic pregnancy	x (x.x)	x (x.x)	x (x.x)	x (x.x)	x (x.x)	x (x.x)	x (x.x)	x (x.x)
Molar pregnancy	x (x.x)	x (x.x)	x (x.x)	x (x.x)	x (x.x)	x (x.x)	x (x.x)	x (x.x)

Country	Live Births (2017)	% of Total live births	Expected N live births of unexposed mothers	Country cap on unexposed pregnancies
Australia	309,142	8.0	48	150
Austria	87,633	2.3	14	136
Belgium	119,690	3.1	19	150
Czech Republic	114,405	3.0	18	150
Denmark	61,397	1.6	10	95
Greece	88,523	2.3	14	138
Italy	458,151	11.9	71	150
Netherlands	169,200	4.4	26	150
Norway	56,633	1.5	9	88
Slovakia	57,969	1.5	9	90
South Africa	989,318	25.6	154	150
Spain	390,024	10.1	61	150
Sweden	115,416	3.0	18	150
Switzerland	87,381	2.3	14	136
UK	755,043	19.6	117	150
Total	3,859,925	100.0	600	NA a

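### The exposure columns in 9.7.2.7 and Appendix G depend on dosing that a pregnancy must survive to receive, so loss percentages cannot be read across them

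*Supplement*

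**What the plan says.** Section 9.7.2.7 requires mothers' results in eight columns. Column (i) is unexposed, (ii) stopped before conception and (iii) first-trimester exposure. The fourth reads "iv) 'exposure in 2 nd /3 rd trimesters". Column (v) is use at conception and in the first trimester with a stop in a later trimester. The last three read "vi) 'exposed throughout pregnancy', (vii) 'exposure during breastfeeding only', and (viii) 'exposure anytime during pregnancy and up to 15 weeks, and breastfeeding". The section adds: "Columns will not be mutually exclusive".

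Appendix G sets these out as a table and heads the eighth column "Exposure during both pregnancy and breastfeeding". Rows for losses, such as "Miscarriage without congenital anomaly", and for stillbirth, termination, ectopic and molar pregnancy appear as n (%) under an N in all eight columns.

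On exposure, section 9.3 states: "In adult subjects a single dose of Repatha ® constitutes exposure". Section 9.7.2.3.2 states: "unexposed subjects are women who have not received Repatha ® during pregnancy and/or breast-feeding". Section 7.2 defines the internal comparator in the same sense. Section 8.2 instead defines the unexposed group for pregnancy outcomes only by the 15 weeks before pregnancy and the pregnancy itself.

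Appendix F counts miscarriage before 22 completed weeks and stillbirth after that, and sets no gestational limit on termination. For infants, 9.7.2.7 stratifies by timing of exposure, including breast-feeding, and section 9.3 lists "Hospitalisations (total number of days hospitalised; number of hospitalisation episodes during the first 12 months".

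**The concern.** A woman can be placed in a late-exposure or breast-feeding column only if her pregnancy lasted long enough for the dose or the stop to happen. If losses are then shown as a percentage of the whole column, the column's survival requirement lowers the percentage regardless of the drug. This is guarantee-time (immortal-time) bias. The documents shown give no denominator of pregnancies still at risk at each stage, and no rule that only doses before the outcome count.

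Section 7.2 offers the unexposed women as reference data for judging exposed pregnancies, the checklist in Appendix B calls this a signal detection study, and annual interim reports go to regulators. A low percentage in (iv) or (v), or a zero in (vii) or (viii), could be taken as reassurance when it follows from the column definition. The anomaly rows are affected too: (vii) and (viii) cannot hold anomalies that ended in loss or termination, so their anomaly percentages describe live births only.

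**Working it through.** The plan gives no loss rate by column, so there is no figure to reproduce. The check is what each column would show with no drug effect. All rates below are assumptions, not figures from the documents:

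- L: total risk of loss or termination
- f: share of those losses after the first trimester
- s: share of live births without pregnancy exposure whose mothers first dose while breast-feeding
- a: share of first-trimester losses in women still on drug
- c: share of pregnancies continuing past the first trimester that stay on drug until they end

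The 300 used for scale is the first-trimester exposure target in section 9.5.

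**Column (iii).** Columns overlap, so women who continue remain here. The proportion is L. At L = 15%: 45 of 300.

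**Column (iv), all ongoing users continuing.** First-trimester losses cannot enter, so the proportion is L·f / (1 − L·(1 − f)). At L = 15%, f = 10%: 0.015 / 0.865 = 1.7%, about 4.5 of 260. Over L = 10–30% and f = 5–30% it runs from 0.6% to 11.4%. It is well below L but not zero.

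**Column (v).** The same exclusion applies, and the pregnancy must also last until the stop date. If stopping is unrelated to loss, its proportion is no higher than that in (iv).

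**Columns (vii) and (viii).** Breast-feeding follows a live birth, so miscarriage, stillbirth, termination, ectopic and molar rows are 0%. The one exception is a multiple gestation with a surviving infant, which the template does not address.

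**Column (vi).** There are two readings for a pregnancy that ends early.
- Throughout means to delivery: first-trimester losses are excluded and their count is 0.
- Throughout means until the pregnancy ended: the proportion is (a·0.9L + 0.1L·c) / (a·0.9L + (1 − 0.9L)·c), with f = 10%. At L = 15%, a = 100%, c = 30%: 0.1395 / 0.3945 = 35%. With a = 50% it is 22%. When a = c it returns to 15%, so losses are over-represented only if a exceeds c.

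**Column (i), 9.7.2.3.2 definition.** Live births first dosed during breast-feeding leave the column and every loss stays: L / (L + (1 − L)·(1 − s)). At L = 15%:
- s = 5%: 15.7%
- s = 10%: 16.4%
- s = 20%: 18.1%
- s = 40%: 22.7%

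Under the section 8.2 definition it stays at 15%.

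**The case against.** The analysis is descriptive, with no inference and no formal comparison of exposed and unexposed women (9.7.2.1, 9.7.2.4). Section 9.7.1.1 calls Appendix G an example template. No separate analysis plan is shown, and one could define column (vi). The overlap of columns protects (iii), the group the study size targets. The zeros in a breast-feeding-only column are plain from its label.

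Much of this stands. It limits the consequence, and a definition of (vi) elsewhere would settle that part. It does not remove the problem. The columns are required by 9.7.2.7 itself, a descriptive percentage can mislead without a test, and overlap puts no early loss into (iv), (v), (vii) or (viii).

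A reader might infer more than the documents support:
- **That no loss or termination can appear in any late-exposure column.** Under Appendix F, second-trimester miscarriages, stillbirths and later terminations can fall in (iv) to (vi). Only (vii) and (viii) exclude loss structurally.
- **That losses pile up in the other columns generally.** Column (iii) shows the true proportion. Column (ii) does not by its label depend on survival, and the plan does not say whether women who resume are moved out of it.
- **That women who continue treatment will look harmed.** This needs one reading of (vi) and assumed continuation shares. The other reading gives the opposite picture.
- **That hospital days before the first dose during breast-feeding are credited to the breast-feeding stratum.** The plan does not say how they are allocated.

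**Conclusion.** The point holds in a limited form. From the definitions alone, (iv) and (v) omit first-trimester losses, (vii) and (viii) show no pregnancy loss, and (vi) has no stated meaning for pregnancies that end early. Loss percentages are therefore not comparable across columns or with column (i).

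With no drug effect, L = 15% and f = 10%, (iv) shows 1.7% where (iii) shows 15%. The shift in (i) is small unless many women first dose while breast-feeding, and it arises only under the 9.7.2.3.2 definition. These sizes rest on assumed rates and on percentages being taken of the column N, as the template's layout implies. The percentages in (iii) are not distorted by this mechanism and no formal test is affected. The matter is worth correcting because the repair is cheap and the table goes to regulators.

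**What to change.** Amend 9.7.2.7 and Appendix G as follows.

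(a) Classify each pregnancy by doses given before its outcome, and state where a pregnancy that ends early belongs in relation to (vi).

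(b) For (iv) to (vi), report losses among pregnancies ongoing at the start of the second trimester, fixed at one stated gestational week. Include second-trimester miscarriages, stillbirths and later terminations. Add an unexposed column with the same denominator. Footnote that (v), and women in (iv) who start late, still require survival to the stop or start date.

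(c) Leave pregnancy-loss rows blank in (vii) and (viii), and use those columns for infant outcomes.

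(d) Define unexposed for pregnancy outcomes without reference to dosing after birth, in line with section 8.2.

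(e) Where event dates exist, show infant events before and after the first dose during breast-feeding separately.

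The cost is wording, one added column and some blanked cells. Denominators in the late-exposure columns become smaller. Section 9.3 lists dose dates and last menstrual period but not expressly a date of loss, and it lists hospitalisations as totals. The Appendix I pregnancy worksheet asks for termination and delivery dates, but section 11 requires it only for exposed women. The eCRF must therefore be confirmed to hold dates of loss, for both groups, and of hospitalisation.
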